In addition to examining whether BA affects smoking outcomes (the “Intervention Hypothesis”: see Figure 1), a secondary objective of the proposed research is to examine the treatment effects of BA on PTSD symptoms and affective distress. Examining these treatment effects will also identify potential mediators of BA on smoking outcomes. Although this initial research is not powered for mediation analyses, such analyses may nevertheless suggest how BA works for smokers with PTSD and provide critical pilot data for future treatment process research. A secondary benefit is that the proposed work will produce additional data on BA as a treatment for PTSD. The following are hypothesized treatment effects of BA that may promote smoking cessation:

PTSD Treatment Effect. Consistent with prior research^{6,7,8,11,19}, we posit that BA will reduce overall PTSD symptom severity. Exploratory analyses will also examine the BA effects on each PTSD symptom cluster (re-experiencing, avoidance, emotional numbing, hyperarousal) to refine analyses of potential mediators. Self-report PTSD symptom severity will be measured at treatment visits and at each follow-up visit. In addition, a structured clinical assessment of PTSD (via the Clinical Administered PTSD Scale; CAPS) will occur at baseline and end-of-treatment.

Negative Affect Treatment Effect. BA has been shown to reduce depressed mood during smoking cessation⁹, and increased engagement in reinforcing activities is associated with decreased negative affect⁵¹. Thus, we posit that BA will decrease negative affect following quitting smoking. We will also explore the effects of BA on other tobacco withdrawal symptoms (e.g., craving) since negative affect may be causally linked with such symptoms. In addition, exploratory analyses will examine the influence of BA on depressed mood because depression often co-occurs with PTSD⁵⁹. Negative affect, depressed mood, and withdrawal symptoms will be assessed at every study visit and follow-up visit. A structured clinical assessment of current depression, in addition to PTSD, will occur at baseline and end-of-treatment.

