The following assessments will be conducted during the study: 1) Screening/diagnostic assessments used to determine inclusion into the study, 2) baseline descriptive assessments, 3) smoking status assessments, 4) treatment effect assessments, and 5) treatment adherence assessments. See Table 1 for the schedule of assessments.

Table 1. Therapy and Assessment Schedule for the Study

	Baseline	Therapy Sessions									Follow-ups		
	V1	V2 Wk -4	V3 Wk -3	V4 Wk -2	V5 Wk -1	V6 Target Quit Day	V7 Wk 1 Post- quit	V8 Wk 2 Post- quit	V9 Wk 3 Post- quit	V10 Wk 4 Post- quit	PA1, 2 Wk 12,20 Post-quit	V11 Wk 26 Post- quit	
In-person Counseling (ST+BA or ST+HSE)		TS1	TS2	TS3	TS4	TS5	TS6	TS7	TS8				
Screening/Diagnostic Assessments													
PTSD phone screen (PC-PTSD)	X*												
Axis I Disorders (SCID-I)	X												
PTSD (CAPS)	X									X			
Depression (SCID-I)	X									X			
Suicidal/Homicidal Ideation Assessment	X												
Medical History	X												
Baseline Descriptive Measures													
Demographics	X												
Smoking history	X												
FTND	X												
WSWS	X												
Smoking Status Assessments													
Smoking/Alcohol use Status		X	X	X	X	X	X	X	X		X	X	
Calendar data		X	X	X	X	X	X	X	X		X	X	
CO assessment	X					X	X	X	X			X	
Cotinine Assessment												X	
Treatment Effects Assessments													
PANAS	X	X		X		X	X	X	X	X	X	X	
PTSD symptoms (PCL)	X			X		X	X	X		X	X	X	
Depressed mood (PHQ-9)	X								X				
Behavioral Activation (BAS)	X				X		X		X		X	X	
WSWS-11	X					X		X		X	X	X	

Tripartite Pleasure Scale	X				X		X			X		X
Snaith-Hamilton Pleasure	X			X		X		X		X	X	X
Stress and Pleasure	X								X		X	X
Treatment Adherence Measures												
Therapist adherence to treatment												
Adherence to nicotine patch and side effects						X	X	X	X		X (Wk 12 only)	
Participant adherence to BA		X	X	X	X	X	X	X	X			

*Occurs at the phone screen, prior to the in-person screening visit; **Follow-ups at Weeks 5 and 26 are in-person, to permit PTSD and depression assessments and abstinence bioverification, respectively. Other follow-ups, at Weeks 12 & 20, are phone assessments (PA).

Screening/Diagnostic Assessments

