PTSD Symptoms. Posttraumatic Stress Disorder Checklist-Military Version (PCL)⁹⁸ is a 17-item self-report scale that assesses PTSD symptom severity. Items are rated on a 5-point Likert scale according to how much the symptom bothered the respondent over the past month. The psychometric properties of this measure are excellent⁹⁸. In addition, a structured clinical assessment of PTSD via the CAPS will occur at baseline and end-of-treatment (V10).

Depressed Mood. We will use the Personal Health Questionnaire Depression Scale (PHQ) to assess depression. The PHQ is a well-validated tool for the assessment of depressive symptoms. The PHQ will be administered during active treatment and follow-up assessments. The depression module of the SCID-I will also be administered at baseline and end of treatment (V10).

Behavioral Activation. The Behavioral Activation Scale¹⁰⁰ assesses the sensitivity of the Behavioral Activation System, an index of the strength of motivation to engage in reinforcing activities (including goal-directed activity). Although those in the ST+BA group will record the actual *frequency* of engagement in reinforcing activities, self-monitoring is an important component of the ST+BA and could introduce poor treatment fidelity if utilized in the ST+HSE group. Thus, we have chosen to measure sensitivity of the Behavioral Activation System, which theoretically is the primary factor affected by BA. Sensitivity of the Behavioral Activation System will be assessed during active treatment and follow-up sessions. The psychometric properties of the Behavioral Activation Scale are strong¹⁰⁰.

Withdrawal. We will monitor withdrawal severity at baseline, throughout treatment, and

follow-up using the Wisconsin Smoking Withdrawal Scale, a 28-item scale that assesses nicotine withdrawal. It will allow for the assessment of the frequency, duration, severity, and temporal variability in withdrawal symptoms.

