We believe the EMA assessment schedule will produce the data needed for the study although it is less intensive (only one assessment per day) than other EMA protocols. In contrast to most research involving EMA, we are not attempting to characterize the relationships among measures at particular points in time (e.g., examining affect before and after individual cigarettes), which would require a much more frequent assessment schedule. Instead, we are interested in whether BA exerts effects on behavior and ratings on a more tonic basis, consistent with BA's putative mechanisms of action, and are using EMA in order to obtain time-stamped measures.

Treatment Adherence Measures

Therapist Competence and Adherence to Treatment. All treatment sessions in both conditions will be audiotaped, and a random selection of 25% (about 2 tapes per participant) of the audiotapes will be rated shortly thereafter by Drs. [name] and [name] to assess therapist adherence to and competence with the treatment protocol. Audio tapes will be maintained in a locked area accessible only the study staff and will be stored at the VA indefinitely, per VA policy. Separate rating checklists developed for the ST+BA and ST+HSE protocols will be used. Kappa will be reported for rated variables.

Adherence to Nicotine Replacement Therapy and side effects. Adherence to the nicotine patch, gum, and lozenge will be queried at each visit following initiation of NRT (Visits 6–9) and during the 12-week post-quit follow up call. Participants will be asked to return unused patches and gum/lozenge, which will be counted at each visit before dispensing new medication. NRT side effects will also be assessed at each visit. Potential differences in NRT use between treatment groups will be examined and incorporated into statistical models if a meaningful relation with outcomes is detected.

[figure not shown]
Adherence to BA. Patient treatment adherence to the ST+BA condition will be assessed by study personnel during weekly counseling sessions.

Study Procedures

Timing of Events

The study involves three basic phases: 1) Study Consent and Baseline; 2) Therapy Sessions; and 3) Follow-up. Figure 4 illustrates the timing of study events, and the procedures associated with these phases are included in the text that follows.

Figure 4: Study Timeline

Study Consent and Baseline

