Randomization Process. After the in-person screening assessment is complete, the participant will be assigned into ST+BA or ST+HSE. The following variables will be blocked in this order: 1) severity of PTSD, 2) depression status (MDD versus no MDD), and 3) bupropion use. Separate randomization tables will also be developed for those presenting via the two different pipelines (VA vs. community [via DVA]). This will ensure that any characteristics that are related to such entities are counterbalanced across groups. Following randomization, study staff will contact the participant to schedule the first treatment session.

Treatment

All participants will attend eight study visits in which they will receive ST+BA or ST+HSE

(V2-V9). The quit day will occur on the same day as the fifth treatment visit (V6: see Figure 4). At the beginning of each visit (prior to the administration of therapy), participants will complete a series of self-report measures that may include assessments of: 1) positive and negative affect (PANAS), 2) PTSD symptom severity (PCL), 3) depressed mood (PHQ), 4) level of behavior activation (BAS), and 5) withdrawal symptoms. Some assessments will not be administered at every visit to reduce assessment burden (see Table 1 for specific assessment schedule). Smoking status (continuous and point prevalence) will be assessed at every in-person visit following the quit date. Sessions may be completed via telemental health (TMH) at a community based outpatient clinic (CBOC) that is closer to a Veteran’s home or via phone in rare cases in which a Veteran is unable to travel a session in person.

Follow-up

All participants will receive follow-up phone calls at Weeks 12 and 20 (PA1 and PA2). They will also attend an in-person post-treatment follow-up visit to receive structured clinical assessments of PTSD and depression (V10). Participants will also attend an in-person follow-up visit at 26-weeks post-quit for nicotine abstinence bioverification (V11). Follow-up assessments will include measures of smoking status, positive and negative mood, PTSD symptom severity, depressed mood, sensitivity of the Behavioral Activation System, and withdrawal (see Table 1 for schedule).

Treatment Conditions

Treatment Conditions Overview

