The experimental treatment group will receive ST+BA, and the contact control group will receive ST+HSE. BA is being examined as an adjunct to ST, with the latter an evidence-based treatment for smoking cessation. Both treatments will be delivered in eight, individual therapy sessions. Treatment sessions 1–4 (V2–V5) will occur prior to the quit day, therapy session 5 (V6) will occur on the quit day, and therapy sessions 6–8 (V7–V9) will occur each week until 4 weeks post-quit (see Figure 4). Participants in the ST+BA and ST+HSE conditions will participate in 20 minutes of identical, standard smoking cessation treatment during each session. The ST+BA condition will include an additional 30 minutes of behavioral activation therapy, and the ST+HSE condition will include an additional 30 minutes of health and smoking education. In addition to receiving ST+BA or ST+HSE, all participants will receive 12 weeks of the nicotine patch and either nicotine gum or lozenge.

Standard Smoking Cessation Therapy (ST)

Participants in both treatment groups will receive a standard, individual smoking cessation treatment based on the 2008 US PHS Clinical Practice Guideline, *Treating Tobacco Use and Dependence*⁸⁶. The investigative team has considerable expertise in delivering behavioral and pharmacological treatments for smoking cessation. Treatment will be delivered in eight, 20-minute individual sessions over an 8-week period, with existing treatment manuals modified for this delivery format (see Table 2). The use of manuals will help ensure that the ST intervention does not differ between treatment arms (which will be checked with treatment fidelity assays). The same smoking cessation treatment has been used successfully in previous CTRI research (e.g., ^{4,46}). This cessation treatment is similar in content to that used at VA facilities¹⁸, increasing the generalizability of the current research.

Table 2. Standard Smoking Cessation Treatment Overview

Therapy Session	Standard Smoking Cessation Therapy Content
Therapy Session 1 (V2)	
 • Provide reinforcement and support for quitting. • Discuss past quit experiences. • Address pros and cons of quitting. • Initiate self-monitoring. • Provide self-help materials (Clearing the Air USDHHS) ¹⁰⁵
Therapy Sessions 2 (V3)	
 • Identify high-risk situations. • Discuss abstinence violation effect. • Develop coping strategies.

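### The text schedules the PHQ at follow-up, but Table 1 marks the PHQ-9 only at V1 and V9 and at none of the four follow-up contacts

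*Combined protocol and SAP*

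**What the plan says.** Two operational statements in the combined protocol and SAP put depressed mood at follow-up. Under Treatment Effect Measures, the Depressed Mood paragraph makes the PHQ the depression scale and says: "The PHQ will be administered during active treatment and follow-up assessments". Under Study Procedures, the Follow-up section says: "Follow-up assessments will include measures of smoking status, positive and negative mood, PTSD symptom severity, depressed mood". It then continues its list and refers to Table 1 for timing.

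The background section gives the analytic purpose, under Negative Affect Treatment Effect: "exploratory analyses will examine the influence of BA on depressed mood because depression often co-occurs with PTSD". The same paragraph says in general terms that depressed mood is measured at all study and follow-up visits.

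Table 1 has one row for the PHQ-9. It is marked in two columns, V1 and V9, and is blank at V2 to V8, V10, the combined PA1/PA2 column and V11. The SCID-I depression row is marked at V1 and V10.

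The Treatment section, which covers V2 to V9, adds: "Some assessments will not be administered at every visit to reduce assessment burden (see Table 1 for specific assessment schedule".

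**The concern.** The Follow-up section lists depressed mood as a follow-up measure and cites Table 1 for the schedule, yet the table has no follow-up mark for the scale that measures it. A coordinator working from Table 1 would give the PHQ-9 at baseline and once more at V9, then never again.

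At stake is the exploratory question of whether BA changes depressed mood. Part of the protocol's own rationale is a late effect: the background section on BA and smoking cessation cites a trial of BA for smoking cessation in which depressed mood was lower with BA at 6 months post-quit. Under Table 1 this trial would have no PHQ at week 26 with which to look for the same pattern. PHQ scores that are not collected at a visit cannot be recovered later.

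**Working it through.** No sample size, power or alpha figure is involved. The check is a count of marks in Table 1, set against the text.

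**Contacts.** Post-baseline: 8 therapy visits (V2 to V9) + V10 + PA1 + PA2 + V11 = 12. Follow-up: V10, PA1, PA2 and V11 = 4. The combined PA column counts as two contacts.

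**Marks by treatment-effect row**, read by column position:

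| Measure | Post-baseline, of 12 | Follow-up, of 4 |
|---|---|---|
| PANAS | 10 | 4 |
| PCL | 8 | 4 |
| Snaith-Hamilton | 7 | 4 |
| WSWS-11 | 6 | 4 |
| BAS | 6 | 3 |
| Stress and Pleasure | 4 | 3 |
| Tripartite | 4 | 2 |
| PHQ-9 | 1 | 0 |

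The PHQ-9 is the only treatment-effect measure with no follow-up mark. The other seven have 2 to 4.

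**Column alignment.** The CAPS and SCID-I depression rows fall at V1 and V10, as the text on those instruments says they should. The PHQ-9 row has the same number of cells as the CAPS, SCID-I and PCL rows, and the PCL row keeps its marks at V10, PA1/PA2 and V11. So the columns are aligned and the follow-up columns were not lost from the table as a whole. This does not prove that no single mark was lost in drafting or in reading the PDF.

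**Text against table.** The PHQ sentence has two halves. V9 is a therapy session, so the active-treatment half is met, though at only 1 of 8 therapy visits. The follow-up half is met at 0 of 4 contacts. The contradiction lies in the second half.

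**Length of the gap.** The Table 1 header puts V9 at week 3 post-quit, which gives 26 − 3 = 23 weeks without a PHQ. Treatment Conditions Overview says that sessions 6 to 8 "will occur each week until 4 weeks post-quit". If V9 is therefore at week 4, the gap is 26 − 4 = 22 weeks.

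**Possible substitutes.** The SCID-I module at V10 is a diagnostic interview and supplies nothing at weeks 12, 20 or 26. The automated calls list PTSD symptoms, affect and withdrawal, but not depressed mood. The PANAS is marked at all four follow-up contacts, but it measures positive and negative affect.

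**The case against.** The strongest reply is that a blank cell in this table is weak evidence of intent. The row "Therapist adherence to treatment" is entirely empty, although the text says that a random quarter "of the audiotapes will be rated shortly thereafter". The smoking-status row has no baseline mark, although the text has smoking measured at baseline. The table's week labels are also unsettled: the header puts V10 at week 4, and the footnote and the payment schedule put it at week 5. The PHQ-9 blanks may therefore be a clerical slip. This stands, and it supports correcting the table.

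A second reply is that the Treatment section allows measures to be skipped to limit burden, so the text could be cut back to match the table instead. That sentence concerns therapy visits. It can explain blanks at V2 to V8, but not absence from every follow-up contact when the Follow-up section itself lists depressed mood. The documents do not state outright which side is the error, but both operational statements point to follow-up collection.

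Three stronger readings are tempting, and the documents do not support them:

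- A reader might infer that PHQ data will be lost. That depends on the table governing delivery. Data and Record Keeping says that questionnaires run through a web-based system and that later visits include mood questionnaires. It does not say which schedule was programmed.
- A reader might count the shortfall as 11 of 12 contacts, from the background statement about all visits. That wording is loose: by the same table it is untrue of negative affect (PANAS, 10 of 12) and withdrawal (WSWS-11, 6 of 12).
- A reader might extend the gap to the main aims. Depressed mood is labelled exploratory, and it is not among the variables named in the Exploratory Mediation Analyses paragraph.

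**Conclusion.** The mismatch is real and minor. The text places the PHQ at follow-up, and Table 1 schedules it at 0 of 4 follow-up contacts and 1 of 12 post-baseline contacts. If the table is followed, the exploratory depressed-mood analysis rests on V1 and V9 alone, with no PHQ in the last 22 to 23 post-quit weeks.

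This assumes that the table as read matches the source and that staff work from it. The primary abstinence outcome, its power, and the PANAS and PCL outcomes are not touched. It is more than a wording matter only because the two schedules lead to different data being collected.

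**What to change.** Mark the PHQ-9 in Table 1 at V10, PA1/PA2 and V11, as the Depressed Mood paragraph and the Follow-up section already state. In the background paragraph on negative affect, replace the general claim about all visits with a reference to the Table 1 schedule.

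The cost is one short questionnaire at four existing contacts that already carry the PANAS, PCL and WSWS-11, with slight extra burden for participants, plus one edited sentence. No new visit is needed, and the sample size and primary analysis do not change.

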One hundred and twenty participants will be enrolled. For inclusion in the study, participants must: 1) report smoking an average of 6 or more cigarettes daily for at least six months; 2) report a desire to quit smoking; 3) meet criteria for *current* PTSD; 4) speak and read English; 5) agree to participate in the study; and 6) be \geq 18 years old.

Participants will be excluded from the study based on the following: 1) meeting criteria for psychotic or bipolar disorder; 2) psychoactive substance abuse or dependence (excluding nicotine dependence) within the past 6 months; 3) inability to give informed, voluntary, written consent to participate; 4) current use of any pharmacotherapy for smoking cessation not

provided by the researchers during the quit attempt; 5) use of non-cigarette tobacco or nicotine products as a primary form of tobacco/nicotine use; 6) being currently suicidal or homicidal, as assessed by VA suicide/homicide template questions administered to all veterans; 7) being medically unable to use the nicotine patch or nicotine gum/lozenge; 8) psychotropic medication changes within 2 months of study initiation and during active treatment; 9) current engagement in evidence-based therapies for PTSD or depression; 10) pregnant or trying to become pregnant; or 11) incarceration.

In addition, we will inform participants that, for research purposes, we prefer that they remain on the same psychotropic medication regimen throughout the trial. However, if it is necessary for a participant to alter treatment for his/her welfare, we will ask the participant to notify us immediately. Such participants will remain in the trial, but primary study analyses will be conducted with such participants excluded.

Any concerns regarding nicotine patch, gum, or lozenge use will be reviewed by the study clinician, who may interview patients should further information be required. All women of childbearing potential will be required to agree to use an approved method of birth control to prevent pregnancy during the period of nicotine replacement therapy (NRT) use. Participants with suicidal or homicidal ideation at screening will be referred for VA psychiatric care, and they will be excluded from the study. Study candidates who express imminent intent for harm to self or others at any point in the study will be referred for VA emergency care.

Assessments

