Measures of Smoking Status. Number of cigarettes smoked each day will be assessed at baseline and every visit. Abstinence (both point-prevalence and continuous) will be assessed on the quit day and at 1, 2, 3, 4, 12, 20, and 26-weeks post-quit day. We will assess long-term outcomes in a manner consistent with the recommendations of the Society for Research on Nicotine and Tobacco (SRNT) Workgroup on Biochemical Confirmation¹. The main outcome analyses are based on 7-day point prevalence abstinence (i.e., reported abstinence for at least the 7 days prior to the assessment). Time-line follow-back (TLFB)⁹⁵ procedures will be used, as in our previous work, to assess continuous abstinence and to establish dates of initial lapse (smoking the first postquit cigarette), relapse (smoking for 7 consecutive days), and total days smoking.

Biochemical Verification. Self-reported abstinence will be biochemically verified at every in-person visit (from the Quit Day through 4 Weeks postquit and at 26-Weeks postquit) by carbon monoxide (CO) analysis of breath samples (8 ppm cutoff⁹⁶). We chose the 26-week postquit follow up to biochemically verify abstinence as this is the smoking cessation outcome time point used in major meta-analytic studies (e.g., ⁸⁶), and it serves as a good index of later smoking outcomes⁸⁶.

In addition to CO verification, urinary cotinine (cutoff value of 20 ng/ml) for stated abstinence of 2 weeks or more (cotinine may be incompletely metabolized before this time) will be assessed at 26-Weeks postquit. All participants will be queried as to NRT use as this could affect cotinine levels. Expired air CO levels will be assessed with a carbon monoxide monitor⁹⁶. Detected values above the stated cutoff scores will be considered indicative of smoking.

Treatment Effect Measures

Positive and Negative Affect. The Positive Affect-Negative Affect Schedule (PANAS)⁹⁷ will be used to assess positive and negative affect. The PANAS is a self-report state mood questionnaire consisting of 10 adjectives describing positive mood states and 10 adjectives describing negative mood states that are rated on 5-point scales ranging from 1 (very slightly or not at all) to 5 (extremely). The PANAS possesses good reliability and validity⁹⁷. Positive and negative affect will be measured at all treatment and follow-up sessions. Anhedonia, the ability to experience pleasure will also be assessed by the Pleasure Activity Scale and Hedonic Tone questionnaires.

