Participants in both groups will begin using the nicotine patch and gum or lozenge starting on the morning of their assigned quit day. Nicotine patch and gum or lozenge will be provided to participants, at no cost, by the Madison VAMC. Consistent with the 2008 PHS Guideline⁸⁶, participants smoking ten or more cigarettes/day will receive 12 weeks of the following patch dosing: 6 weeks of 21 mg, 4 weeks of 14 mg, and 2 weeks of 7 mg nicotine patches. Participants smoking less than ten cigarettes/day will receive 12 weeks of the following patch dosing: 8 weeks of 14 mg and 4 weeks of 7 mg nicotine patches. Participants may taper down on patch dosage more slowly if needed as suggested by the 2010 VHA Tobacco Use Cessation Treatment Guidance. They will be instructed to apply one patch daily. As per the PHS Guideline, VHA Guideline, and package insert, gum/lozenge dose will be based on cigarettes smoked per day. Participants who smoke less than 25 cigarettes/day will only receive 2-mg gum/lozenge; participants smoking 25 or more cigarettes/day will receive 4-mg gum/lozenge. Participants will be told to try to use one piece of gum every 1-2 hours. However, participants will also be told that they may not be able to take a full, recommended dose of oral NRT given their conjoint use of the patch. Participants will be urged to use *at least* 5 pieces/day, unless this amount of use produces negative (toxic) effects. All participants will be given complete instructions on proper NRT use⁸⁶ and on signs of nicotine overdose/toxicity. Medication usage and side effects will be assessed at all visits. [name], the VA smoking cessation coordinator, clinical pharmacist, and study clinician, will recommend dosage/use alterations as per good clinical practice if the participant experiences symptoms of nicotine toxicity or side-effects. Changes in recommended medication use will be considered in analyses of adherence outcomes. Participants will be asked to continue taking the medication for the full 12 weeks unless they are smoking regularly and heavily (≥ 10 cigarettes per day every day).

Standard Smoking Cessation Treatment Plus Health and Smoking Education (ST+HSE)

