In accordance with VA policy, in the case of reporting incidents, i.e. theft or loss of data or storage media, unauthorized access of sensitive data or storage devices or non-compliance with security controls, the Information Security Officer and Privacy Officer will be notified within one hour to determine an appropriate course of action.

Statistical Considerations

Power considerations

Estimated effect sizes for the primary treatment comparison and the power available to detect these effects with two-tailed tests are provided below for the total $N = 120$ participants with 25% attrition, using intent-to-treat approach. We computed power for the GLMM longitudinal analysis using a SAS macro developed by Dang and colleagues¹⁰⁸.

Specific Aim 1: [name] recent trial of BA for smoking cessation in smokers with symptoms of depression showed that 19% of smokers who received ST+BA were abstinent at 6-months post-quit, relative to those who received a contact-control smoking cessation treatment (0% abstinence rate at 6-months post-quit). For a treatment of this intensity (ST+BA), we believe that an improvement of at least 15% at 26-weeks post-quit would be sufficiently large to support additional research. For the current study, we predict that 6-month point prevalence abstinence rates will be 20% for ST+BA and approximately 5% for ST+HSE. We computed power for the GLMM longitudinal analysis using a SAS macro developed by Dang and colleagues¹⁰⁹ with the following parameters: $N=45$ per group; 5 time-points; drop-out rate of 0.25; 5% vs. 20% treatment effect over time; random effects variance=1; and within-subject correlation=0.6. Power for this scenario is 0.85. Even though power estimates have accounted for an estimated 25% attrition for a sample of $N=90$, we increased the sample size by 30 participants ($N=120$) to ensure that we have sufficient statistical power (which accounts for 25% attrition). Thus, the current study will have strong statistical power in the GLMM analyses.

Data and Record Keeping

Data elements will be collected and stored during the screening assessment and all visits and phone assessments. During the screening session, data resulting from structured clinical interviews assessing Axis I Disorders will be collected and stored. In addition, questionnaires measuring mood, medical history, smoking characteristics, craving, withdrawal symptoms, CO levels, behavioral activation, and demographic information will be collected and

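### An outcome-triggered rule lets nicotine replacement use, recorded only after randomisation, into unnamed models, and nothing keeps an Aim 1 comparison without it primary

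*Combined protocol and SAP*

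**What the plan says.** The sentence at issue closes the paragraph on NRT adherence and side effects, under Treatment Adherence Measures: "Potential differences in NRT use between treatment groups will be examined and incorporated into statistical models if a meaningful relation with outcomes is detected".

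The surrounding text bears on it as follows.

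- **Timing.** Under Randomization Process, assignment follows the screening visit (V1). Under Treatment Conditions Overview, "Treatment sessions 1–4 (V2–V5) will occur prior to the quit day". Under Nicotine Replacement, "Participants in both groups will begin using the nicotine patch and gum or lozenge starting on the morning of their assigned quit day", which is V6.
- **Measurement.** NRT use is queried, and returned product counted, at V6–V9, with a further query at the week-12 call. The automated evening calls also ask about it, and NRT use is queried in connection with the week-26 cotinine test.
- **Dependence on arm.** Table 3 lists adherent NRT use as a topic of HSE session 5, held on quit day.
- **Dependence on smoking.** Under Nicotine Replacement, "Participants will be asked to continue taking the medication for the full 12 weeks unless they are smoking regularly and heavily", defined there as at least 10 cigarettes every day.
- **Outcome and model.** Under Smoking Status Assessments, "The main outcome analyses are based on 7-day point prevalence abstinence". Power considerations describes N=120 "with 25% attrition, using intent-to-treat approach. We computed power for the GLMM longitudinal analysis". Neither section lists covariates.
- **A possible limit.** Also under Nicotine Replacement: "Changes in recommended medication use will be considered in analyses of adherence outcomes".

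**The concern.** Aim 1 compares abstinence between two assigned treatments. A variable recorded after treatment has begun, which either treatment may change, can lie on the path from treatment to abstinence. It can also be partly a result of smoking. Conditioning on it replaces the total effect of assignment with a different quantity.

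The trigger adds a second problem. NRT use enters only if it is seen to relate to outcome, with meaningful left undefined and several candidate measures available. The analyst would then hold adjusted and unadjusted estimates, with no rule fixed in advance for which one answers Aim 1.

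**Working it through.** **1. The plan's own figure.** Power considerations states 0.85 for 45 per group, 5% v 20%, 5 time points, 25% dropout and correlation 0.6. Take a Wald test of the time-averaged difference in proportions with AR(1) correlation, dropout rising evenly to 25%, and two-sided alpha 0.05. The structure, dropout pattern and alpha are my assumptions. The effective number of observations per person is 1.844.

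SE = √[(0.20×0.80 + 0.05×0.95)/(45×1.844)] = √(0.2075/82.97) = 0.0500. Power = Φ(0.15/0.0500 − 1.96) = 0.851.

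The stated figure reproduces on these assumptions; exchangeable correlation gives 0.749. The point does not rest on this. It shows that the planning effect is the contrast between assigned arms, with no NRT term.

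**2. Order of events.** V1, then randomisation, then V2–V5 (four arm-specific sessions), then V6 (NRT starts and is first recorded). No NRT-use measure can predate assignment or the first four sessions.

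**3. Size if applied to Aim 1.** Inputs from the plan: 20% and 5%. The unadjusted odds ratio is (0.20/0.80)/(0.05/0.95) = 4.75 and the risk difference is 0.15. Assumed: a yes/no adherence variable with proportion m in each arm, NRT-abstinence odds ratio θ of 2 or 4 in both arms, and no unmeasured common cause.

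In each arm, let p0 and p1 be abstinence in non-adherers and adherers. Solve m·p1 + (1−m)·p0 = 0.20 (BA) or 0.05 (HSE), with p1/(1−p1) = θ·p0/(1−p0). The adjusted odds ratio is the BA odds at p0 over the HSE odds at p0.

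Example, 60% BA v 40% HSE, θ=2. BA: p0=0.1375, p1=0.2417 (0.6×0.2417 + 0.4×0.1375 = 0.200). HSE: p0=0.0364, p1=0.0703 (0.4×0.0703 + 0.6×0.0364 = 0.050). Ratio = (0.1375/0.8625)/(0.0364/0.9636) = 4.21 with unrounded values.

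| Adherence BA v HSE | Adjusted OR, θ=2 / θ=4 | Adjusted risk difference, θ=2 / θ=4 |
|---|---|---|
| 60% v 60% | 4.82 / 4.99 | 0.150 / 0.150 |
| 60% v 50% | 4.52 / 4.43 | 0.143 / 0.138 |
| 60% v 40% | 4.21 / 3.88 | 0.136 / 0.125 |
| 70% v 40% | 3.95 / 3.45 | 0.130 / 0.114 |
| 40% v 60% | 5.54 / 6.56 | 0.164 / 0.177 |

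With equal adherence the risk difference does not move; the small rise in the odds ratio is non-collapsibility. With an unmeasured common cause of adherence and abstinence added, the unequal-adherence risk differences span 0.103 to 0.188.

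**4. Letting relapse shorten NRT use.** Assume exponential relapse reaching 20% v 5% abstinent at week 26, with 25% / 50% of relapsers stopping NRT at relapse. A week-26 logistic model adjusted for weeks of NRT gives about 4.7 / 4.5 if non-relapse stopping is 30% in both arms. It gives about 4.2 / 3.8 with 20% BA v 50% HSE (stopping times spread evenly over 12 weeks), and about 5.0 to 5.1 when those rates are reversed. The direction again depends on how NRT stopping differs by arm.

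**5. Effect on the decision.** Take the step 3 setting with 60 per arm. Let the rule fire when NRT use differs by arm and also relates to outcome, each at p<0.05 (assumed). With 60% v 40% adherence it fires in 14% / 37% of 1,500 simulated trials (θ = 2 / 4). Power moves from about 0.76 to 0.73 / 0.66, and adjusted and unadjusted tests disagree on significance in 12% / 18%. Reversed, with θ=4, power rises from 0.76 to 0.82. These are single-endpoint figures, not the planned GLMM.

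**The case against.** The strongest reply is that the sentence was never meant for Aim 1. It sits among adherence measures. The nearby text on changes in recommended medication use refers to adherence analyses, and neither the aims, the outcome definition nor the power section mentions NRT adjustment. This has some force: application to Aim 1 is a reading, and the documents do not state it. But the text on adherence analyses concerns a different item, and the trigger in the challenged sentence is a relation with outcomes, without restriction. Intent-to-treat says who is analysed; it does not exclude covariates.

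A second reply is that harm is small. In a random-intercept GLMM with random-effects variance 1, and 25% / 50% of relapsers stopping NRT, the conditional odds ratio goes only from 5.71 to 5.68 / 5.61, with no loss of power. That result stands for its inputs, but it fixes non-relapse stopping at 30% in both arms. The sentence is written for the case where use differs between arms.

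The link from smoking to NRT use is also limited, and this stands. The request to continue is lifted, but stopping is not directed. Entry requires that participants "report smoking an average of 6 or more cigarettes daily for at least six months", so some can return to their usual smoking without meeting the exception.

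**Conclusion.** The point holds as a gap in specification that should be closed. Followed as written, the rule can change what Aim 1 estimates and leaves the choice of reported effect until after outcomes are seen.

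A reader might infer more, and the documents do not support it:

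- **That the plan commits to adjusting Aim 1 for NRT use.** It does not say so.
- **That adjustment would weaken the BA effect.** It could equally inflate it, since NRT adherence is an HSE topic and use may be higher in that arm.
- **That the shift is known to be negligible or large.** With no NRT adherence figures in the documents, the range from about 3.5 to 6.6 around 4.75 (step 3) illustrates assumed inputs and is not a forecast.
- **That type I error is clearly inflated, or clearly safe.** In null runs with unequal adherence (10% abstinent in both arms), rejection under an outcome-relation trigger was about 0.06–0.12, against 0.05–0.08 unadjusted, with Monte Carlo error about 0.01. This settles neither claim.

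The conclusion that the primary comparison is left open does not depend on any of these assumed figures.

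**What to change.** Replace the sentence with three statements.

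1. The primary Aim 1 comparison is by assigned arm and does not include NRT use as a covariate.
2. NRT use is reported descriptively by arm.
3. Any NRT-adjusted abstinence model is a labelled sensitivity or exploratory mediation analysis, with its NRT measure (for example product counts at V6–V9, or use to week 12) named in advance.

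If the intention was always to confine the rule to adherence analyses, the first statement makes that explicit.

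The cost is wording and minor analysis work; the variables are already collected. No view is taken on the NRT continuation rule.
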